## **Study Protocol**

The study is designed to test the effectiveness of online versions of the Memory & Aging Program (MAP) and Goal Management Training (GMT), on the measures used for in-person MAP and GMT in healthy older adults experiencing subjective cognitive impairment.

### **Background**

Normal aging is associated with decline in some aspects of memory, such as memory for recent information (e.g., where did I put my glasses?), associations (e.g., what was your name again?), and intentions (e.g., why did I come in this room?), as well as changes to executive functions, such as sustaining attention, problem-solving, and planning. These age-related cognitive changes can be a source of frustration and anxiety and may be a risk factor for reductions in everyday functioning, which threatens the independence of otherwise healthy older adults. Secondary prevention programs that target positive adaptation to age-related cognitive changes, including lifestyle behaviour change to maximize cognitive health and compensatory strategies for mitigating the functional impact of normal memory & executive functioning change, are a promising avenue to enhance the health and wellness of our aging population.

The Baycrest Memory and Aging Program (MAP) is an education and intervention program for older adults experiencing normal age-related memory changes. The program is offered quarterly at Baycrest. Over 1,000 clients have participated since its inception in 1997. The goals of the program are to (a) increase participant knowledge about memory and aging, (b) expand participants' repertoire of evidence-based strategies for learning and remembering, (c) increase participant confidence in memory ability, (d) foster adoption of healthier lifestyle practices, and (e) reduce intention to use unneeded health care resources. Two prior formal program evaluation studies have demonstrated efficacy of the MAP in achieving these stated goals (Troyer, 2001; Wiegand, Troyer, Gojmerac, & Murphy, 2013). Goal Management Training™ (GMT) is another evidence-based cognitive intervention program developed at Baycrest that targets executive functioning. The program includes an engaging narrative that increases awareness about these cognitive abilities, teaches strategies to help control automatic processing that hinders flexibility of cognitive performance, provides practice exercises and assignments that help internalize and harness these strategies, and teaches meditation techniques that promote mindfulness (Levine, et. al., 2000; Levine, et. al., 2007; Levine, et. al., 2011).

As in any in-person intervention, participation may be restricted for some individuals because of obstacles that prevent them from attending sessions at Baycrest, such as physical disabilities, transportation impediments, scheduling difficulties, or living outside of the Toronto area. Recently, online versions of the MAP and GMT were designed to overcome some of these limitations and increase the outreach of the program to a broader audience. These versions consist of weekly modules that relay the material in a variety of forms including videos, animations, interactive games, discussion boards, live chats, and homework assignments. The current project seeks to evaluate participant outcomes following the online version of the MAP and GMT using a randomized controlled pretest-posttest design.

## **Objectives**

The online program was designed to be similar to the in-person version in terms of content and activities to provide similar levels of engagement. We therefore expect similar outcomes, namely:

For MAP: that compared to the control groups, participants in the intervention group will demonstrate greater knowledge about memory and memory strategies, increased confidence and satisfaction with their memory, healthier lifestyle behaviors, and decreased intentions to seek unnecessary medical attention;

And for GMT: that compared to control groups, participants will demonstrate increased executive functioning and decreased cognitive failures.

## **Method**

### **Study population**

200 healthy community-dwelling older adults will be recruited by newspaper and online advertisements (see Appendix).

Inclusion criteria:

[figure not shown]
- (a) Age 60+
- (b) Available to participate in all testing and intervention sessions and access to a computer
- (c) Computer familiarity
- (d) Cognitive complaint/concern/frustration

Exclusion criteria:

- (a) Health conditions with major effects on cognition, including a current or previous history of stroke, brain surgery, or diagnosed neurological disorder;
- (b) Dependence in instrumental activities of daily living
- (c) Cognitive impairment, defined as performance below cutoff for cognitive impairment on a standardized cognitive screening measure, the modified Telephone Interview for Cognitive Status (Welsh et al., 1993)
- (d) Affective impairment, defined as performance below cutoff for depression on standardized depression screen, the Geriatric Depression Scale (Yesavage et al., 1983)

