### **Study Procedures**

Study procedures are illustrated in figure, below. The estimate of the number of participants reflects the expectation of attrition due to the length of the study. Potential participants will be screened online and over the telephone for inclusions and exclusions as outlined above. Informed consent, pretest, posttest, and follow-up testing sessions will be completed online. The online cognitive training protocols are largely completed online from the participants' home or other location of their choosing. All protocols include interactive components; in some cases this involves telephone calls and/or online discussion with research personnel. Total participation duration is 17 weeks. Data collection is planned to be completed within one year of REB approval.

Interested participants who replied by email to the study advertisement (see Appendix) will be emailed the information sheet portion (excluding the signature section) of the informed consent, and will be asked to complete the online screening form and phone screening interview (see script in Appendix). Eligible participants will then be emailed a link to an online pre-test assessment. As the bulk of the study will be taking place online, participants will accept provisions of the study through an online consent form.

Following completion of the pre-test assessment session, participants will be randomly assigned to one of four groups according to a blocked randomization scheme (stratified on age, gender, and education) created by a study team member unknown to participants or otherwise involved in data collection procedures. Participants will be informed of their group allocation by email and then begin the assigned program at their convenience, immediately following the completion of the pretest.

The intervention groups are as follows:

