4. BrainHQ: is a commercial brain training platform that has a variety of short tasks. We will be using a customized training regimen that focuses on games designed to hone attention, memory, and brain speed. The program involves about an hour of training on this platform per week, which consists of a series of short games (5 min each) for half an hour at a time. The program includes pre/post online assessment of cognition.

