#### Pre-/Post-test measures

Measures were selected based on previous findings from the in-person MAP and GMT evaluations. Most are standardized questionnaires and/or tasks, and most have been used previously, as noted below, and during preliminary pilot testing of the program. All measures will be administered during each testing session, and all will be administered online.

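### Eligibility does not exclude earlier MAP or GMT participants, who may have less left to gain in the matching arm, so the tested effect can be diluted (minor)

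*Combined protocol and SAP*

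**What the plan says.** Recruitment is open: "200 healthy community-dwelling older adults will be recruited by newspaper and online advertisements" (Study population). The inclusion criteria cover age, availability and computer access ("Available to participate in all testing and intervention sessions and access to a computer"), computer familiarity, and a cognitive complaint. The exclusion criteria cover health ("Health conditions with major effects on cognition, including a current or previous history of stroke, brain surgery, or diagnosed neurological disorder"), dependence in daily activities, cognitive impairment and depression. None mentions earlier cognitive training of any kind.

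Study Procedures ties screening to that list: "Potential participants will be screened online and over the telephone for inclusions and exclusions as outlined above". Randomisation follows the pretest and is stratified on age, gender and education. Under Statistical analyses, the covariates named for exploration are age, engagement, subjective cognitive impairment and computer familiarity. That list is open-ended, but earlier exposure is not on it.

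Three places show that earlier exposure is possible:

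- Background, on MAP: "The program is offered quarterly at Baycrest. Over 1,000 clients have participated since its inception in 1997". The Objectives section adds that the online version was designed to resemble the in-person one in content and activities.
- Pre-/Post-test measures says most measures have been used before, "and during preliminary pilot testing of the program". It gives no number of pilot participants.
- Study Procedures says BrainHQ, the comparator programme for GMT, "is a commercial brain training platform that has a variety of short tasks".

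**The concern.** MAP is aimed at older adults with memory concerns, and the trial recruits people aged 60 or over with a cognitive complaint. As the criteria stand, a former MAP client, a former GMT participant or a pilot participant is eligible.

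Two of the six primary outcomes, the memory knowledge quiz and the memory strategy toolbox, measure material that MAP teaches. Someone who has already learned it starts higher and may improve less when taught it again. The planned test is the interaction between group and pretest-posttest scores, so smaller gains in the intervention arm translate directly into a smaller tested effect. The same reasoning applies to GMT alumni in the GMT arm.

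The plan states no effect size, power or attrition rate, so no margin to absorb such a loss can be shown. Exposure is also not recorded under the stated plan. A null result could then not be separated from dilution, and no analysis restricted to unexposed participants would be possible.

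**Working it through.** **The plan's own figure.** The total of 200 cannot be reproduced. No significance level, power, effect size, standard deviation or attrition rate is given. What follows is an illustration on stated assumptions.

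**Inputs.**

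- From the documents: 200 participants; four arms; pretest before randomisation; test of group by time.
- Assumed: equal allocation (200/4 = 50 per arm, before attrition); two-sided 0.05; 80% power for the undiluted effect; standard deviation unchanged by exposure.
- Assumed: p, the share with earlier exposure to the tested programme; r, the share of the usual gain that an exposed person can still make (0 or 0.5).

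**Step 1: which arm loses.** Let the full gain be g = 1. Suppose that exposed people already have g at pretest, keep it, and gain nothing more. With p = 10% in both arms:

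- Intervention: pretest 0.10, posttest 0.90 + 0.10 = 1.00, change 0.90.
- Control: pretest 0.10, posttest 0.10, change 0.
- Interaction: 0.90 − 0 = 0.90 of the full effect.

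With exposure only in the controls, the interaction is 1 − (0.10 − 0.10) = 1.00. With exposure only in the intervention arm, it is 0.90 − 0 = 0.90. The whole loss comes from the intervention arm.

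**Step 2: size of the dilution.** Diluted effect / full effect = 1 − p(1 − r). The sample size needed to offset it is multiplied by 1/[1 − p(1 − r)]². With r = 0 this is 1/(1 − p)²; for p = 10%, 1/0.90² = 1.23.

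**Step 3: power.** The standardised effect detectable with 80% power at 50 per arm is (1.96 + 0.84) × √(2/50) = 0.56. Multiplying by the ratio in step 2 gives:

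| Assumed p | Effect kept, r = 0 | Diluted d | Power | n per arm for 80% | n multiplier | Effect kept, r = 0.5 | Power, r = 0.5 |
|---|---|---|---|---|---|---|---|
| 2% | 98% | 0.549 | 78.4% | 53 | 1.04 | 99% | 79.2% |
| 5% | 95% | 0.532 | 75.9% | 56 | 1.11 | 97.5% | 78.0% |
| 10% | 90% | 0.504 | 71.3% | 62 | 1.23 | 95% | 75.9% |
| 20% | 80% | 0.448 | 61.1% | 79 | 1.56 | 90% | 71.3% |

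Because the undiluted effect is set to give 80% power, the power figures are the same at 40 per arm. Only the detectable effect changes, to 0.626.

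**Step 4: BrainHQ.** Here the exposure is to the comparator. Earlier users randomised to BrainHQ may gain less there, which lowers the control change and widens the GMT-minus-BrainHQ contrast. Any overlap that lowers the gain of earlier users in the GMT arm would narrow it. The ratio in step 2 does not describe this case, and the net direction is unknown.

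**The case against.** The strongest case for leaving the plan as it stands has four parts.

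- **Exposure may be rare.** Recruitment is by open advertisement, not from a client list, and the online versions are meant to reach people who cannot attend in person. The documents give no exposed share. This stands: nothing in them supports a share of 10% or more.
- **Zero further gain is a worst case.** MAP exposure may date back to 1997, the online content is described as similar, not identical, and only two of the six primaries test directly taught material. This stands too, and is why r = 0.5 is shown.
- **Broad eligibility is defensible and the dilution is conservative.** Exposure is balanced in expectation and costs power without creating false positives. This is right for MAP and GMT exposure. It lowers the priority, but does not explain why exposure goes unrecorded.
- **The question may already be asked.** The advertisement and telephone script are in an appendix not in the text reviewed, and a figure beside the inclusion list is missing. A screening item there cannot be ruled out. Even so, screening is said to follow the listed criteria, so such an item belongs among them.

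A reader might also infer that former MAP clients in the test-retest arm contaminate the control group. That would need a mechanism acting between pretest and posttest. The pretest precedes randomisation and the analysis tests change, so stable earlier exposure cancels (step 1). Training taken up during the trial would be a separate matter.

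**Conclusion.** The point holds as a minor one. On the text reviewed, earlier MAP or GMT participation is not excluded, stratified on or named as a covariate, and it can shrink the interaction through smaller gains in the matching intervention arm. At assumed shares of 2% to 5% the loss is small: power of 78.4% to 75.9% instead of 80% if nothing more is gained, and 79.2% to 78.0% if half the gain remains. At 10% with no further gain, power is 71.3%, which is material, but that share is an assumption. All power figures rest on 50 per arm, two-sided 0.05 and a base of 80%, none of which the plan states.

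Two stronger conclusions are not supported. The documents do not show systematic bias between arms, since randomisation balances exposure in expectation. Nor do they show that earlier BrainHQ use dilutes the GMT contrast, since it could move that contrast either way.

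**What to change.** Add a fifth exclusion criterion to Study population: previous participation in MAP or GMT, whether in person, online or as a pilot participant. Ask it as one item on the online screening form, unless the appendix script already does. In that case, add only the criterion.

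Record earlier BrainHQ use at screening without excluding for it. State under Statistical analyses that the GMT-BrainHQ comparison will be repeated in participants without earlier BrainHQ use, as a sensitivity analysis.

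The cost is one screening question, one line in the eligibility list and one sentence in the analysis plan. The downside is that a few volunteers are turned away.

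### As worded, exclusion criterion (d) appears to point the wrong way: its definition of affective impairment describes people who screen negative for depression

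*Combined protocol and SAP*

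**What the plan says.** The Study population section sets the target as follows: "200 healthy community-dwelling older adults will be recruited by newspaper and online advertisements". Two of its four exclusions rest on screening instruments and share one sentence pattern.

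- Criterion (c): "Cognitive impairment, defined as performance below cutoff for cognitive impairment on a standardized cognitive screening measure". The instrument is the modified Telephone Interview for Cognitive Status.
- Criterion (d): "Affective impairment, defined as performance below cutoff for depression on standardized depression screen, the Geriatric Depression Scale".

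The Study Procedures section makes these the working rules for entry: "Potential participants will be screened online and over the telephone for inclusions and exclusions as outlined above". It also refers to an online screening form and a phone script in an Appendix. That Appendix is not part of the text available for this review. The text that is available gives no version, scoring direction or numeric cutoff for the Geriatric Depression Scale, and it does not mention the scale again.

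**The concern.** A cutoff for depression is ordinarily the threshold that a person must reach to be classed as screening positive. Someone below it has screened negative. Criterion (d) nevertheless gives that person the label of affective impairment and lists the state as a reason for exclusion. The likely cause is that the sentence was carried over from (c) without reversing the direction.

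This matters because (d) is an entry rule and not background text. A form or script built directly from it would inherit its direction. The rest of the plan would be unlikely to reveal the error:

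- No depression measure is listed among the primary or secondary outcomes.
- Randomisation is stratified on age, gender and education only.
- Mood is not among the covariates named for exploration in the Statistical analyses section.

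Criterion (d) is therefore the only stated control on depression. Several primary outcomes are self-report questionnaires on memory satisfaction, dysexecutive problems and everyday cognitive failures, and these plausibly vary with mood.

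**Working it through.** No arithmetic applies. The plan states no figure on this point, and the claim depends on no sample size, power or alpha input. The check is to compare (d) with its own label, with (c), and with the target population under each way of reading it.

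**Inputs from the documents**

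- Label of the excluded state in (d): affective impairment.
- Direction word in (d): below the cutoff. It is the only direction given.
- Condition the cutoff refers to: depression, on an instrument described as a "standardized depression screen, the Geriatric Depression Scale".
- Target population: healthy older adults, stated in the opening Study Protocol paragraph and again under Study population.

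**Input that is assumed**

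- Scoring direction of the Geriatric Depression Scale. The documents do not give it. The description of the instrument as a depression screen with a cutoff for depression fits higher-is-worse scoring, but does not state it.

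**Readings of (d)**

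| Reading | Who is excluded | Agrees with the label and the healthy population? |
|---|---|---|
| 1. Literal (score below cutoff), higher score = more symptoms | Those who screen negative | No |
| 2. Literal (score below cutoff), lower score = more symptoms | Those who screen positive | Yes |
| 3. Non-literal: below taken to mean on the impaired side, whatever the scoring | Those who screen positive | Yes |

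**Comparison with (c)**

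On a cognitive screen, a low result is naturally the poor one, so the literal reading and the impaired-side reading of (c) coincide and no conflict arises. In (d) they coincide only if low scores mean more symptoms. Under higher-is-worse scoring they give opposite decisions for every person screened.

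**Result**

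The definition in (d) is inverted under reading 1, that is, literal wording together with higher-is-worse scoring. The label and the target population show that the exclusion of screen-positives was intended. Nothing else in the supplied text gives a number or a direction that would override the word below. Even with no assumption about scoring, the criterion as supplied cannot be applied reproducibly, because a screener has to compare a score with a value and know which side is excluded.

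**Effect on the analysis if reading 1 were implemented**

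Participants are randomised after the pre-test, and the planned test is the group-by-time interaction. A change in mood common to both arms of a comparison does not produce that interaction. Only a mood response that differs between arms would contribute to it. That would still be a consequence of allocation, so it would affect interpretation more than the validity of the contrast. The main loss is in who was enrolled and to whom the results apply.

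**The case against.** The strongest case on the other side has four parts.

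1. **The intent is plain.** The item is an exclusion, is headed affective impairment, and sits in a study of healthy adults. The criterion speaks of performance, not score, and in (c) the same construction means being in the impaired range. A screener who reads the whole sentence would probably exclude the right people. This stands as evidence of intent, and it makes inverted screening less likely. It does not repair the rule, whose only direction word is the one that conflicts with the label.

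2. **The scoring direction is not in the documents.** This stands. The conclusion has to be stated as conditional on higher-is-worse scoring.

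3. **The screening form and script are not visible.** This also stands. The version, cutoff and direction may be set out in the Appendix, so they cannot be called absent from the plan. A reader might infer from the wording that the trial did enrol people with depression and turn away those without it. The documents do not support that: nothing supplied shows how the form or script applied the scale, in either direction.

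4. **The statistics are untouched.** No sample size, error rate, endpoint or model depends on this. A reader might go further than the point allows and infer that the group comparison would be biased, or attach a percentage of volunteers wrongly admitted or refused. Randomisation largely answers the first. The second would need a screen-positive rate, and the documents give none.

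**Conclusion.** The point holds as an error in the definition of an eligibility criterion. Under higher-is-worse scoring, which is an assumption consistent with the protocol's wording, criterion (d) read literally selects the opposite of what its label and the target population require. The consequence is conditional on literal application: the wrong population would be enrolled, people who screen positive for depression would pass the screen, and the findings would not carry over to healthy older adults. The between-group comparison would remain largely protected. The effect cannot be quantified from the documents, and actual inversion of screening is not shown. Because this is an operative entry rule that no other part of the supplied text corrects, it should be put right and not left to the screener's judgement.

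**What to change.** - Reword (d) so that its definition agrees with its label and people who screen positive for depression are the ones excluded.
- State the version of the Geriatric Depression Scale, its scoring direction and the numeric cutoff. Say whether a score equal to the cutoff counts as positive, since the documents do not settle this. If the Appendix already holds these details, refer to it from the criterion.
- Leave the direction of (c) unchanged.
- Check that the online screening form and the phone script apply the correct direction to each scale separately. If screening has already begun, confirm from the screening records which direction was used.

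The cost is a one-sentence amendment and a check of two screening documents. It needs no extra participants, no new data collection and no change to the analysis.
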